
Objective(s):
	
 - External validation of pre-existing prognostic scores of traumatic haemorrhages at different times of care (Scene of Injury, admission at the trauma room) in order to assess their overall performance, discrimination and calibration in the prediction of massive transfusion and haemorrhagic death. - Comparison of score performances (Overall performance, discrimination and calibration).

Outcome(s):
	
Primary study outcome :
 
 - Massive transfusion defined by a transfusion equal to or greater than 10 Red blood cell (RBC) / 24 hours or ≥ 3 RBC in the first hour if available in the Swiss Trauma Registry. 
Secondary study outcome :
 
 - Death due to bleeding (if available in the registry) - Early death (< 24 hours) - Coagulopathy at admission defined by INR > 1.2, quick TP < 70% or Fibrinogen < 1.5 g/L (6,7,8)

Study design:
	
Observational non-interventional study based on a multicentric anonymized registry

Inclusion / Exclusion criteria:	
Study population: All adult trauma patients treated at twelve Swiss trauma centres Level I from 01.01.2015 to 31.12.2019 with eligible criteria of the Swiss Trauma Registry (STR) are included. All data from the register are anonymised without any access to medical files. The identity of the trauma patients, date of birth, address and trauma scene location are unknown (as mandatory by the swiss law: Art. 2 ORH).
 
Inclusion criteria:
 
- Age > 16 years old- ISS (Injury Severity Score) ≥ 16 and/or AIS head (Abbreviated Injured scale) ≥ 3 
Exclusion criteria:
 
- Age < 16 years old- ISS < 16 and or AIS < 3- Isolated Burns (including electric shock) or if the burn is clearly the primary injury- Patients arriving at the trauma room with no sign of life and no diagnostic/therapeutic measures have been initiated for them- Choking or hanging patient without any other injury.- Drowning patients
--	---

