4.4 Assumed confounding covariate

The majority of the requested variables from the STR are inevitably correlated, as most relate to the haemodynamic status of the patient and the trauma severity. The values of the variables can be confounded by unmeasured factors, such as environmental, genetic or psychological influences. Therefore, the investigators provide an example of possible confounding variables:

- Clinical examinations in prehospital settings (i.e. heart rate, systolic blood pressure, respiratory rate, Glasgow Coma scale) are assumed to be confounded by:
 - Quality of the measurements, stress, pain and anxiety. These confounding covariates should be minor for the statistical analysis.
- Clinical examinations at hospital admission (i.e. vitals signs) are assumed to be confounded by:

- Quality of the measurements, administration of inotropes and/or vasopressors during transport, administration of propofol (negative inotropic effect), induced comas and the need for mechanical ventilation.
- Because some patients will not survive long enough to receive 10 red blood cell units, massive transfusion is subject to misclassification. To correct this misclassification, the investigators add in the massive transfusion definition the use of ≥ 3 RBC administered in the first hour (if the variable is available in the registry).
- The trauma-induced coagulopathy as secondary outcome is assumed to be confounded by anticoagulant treatments. To counteract the confounding covariate, the investigators will include the fibrinogen < 1.5 g/L in the definition of trauma-induced coagulopathy. The investigators will also define a subgroup of patients with anticoagulant treatment or not.

The investigators acknowledge that there will be residual confounding in our dataset due to the presence of unmeasured confounding, some of which is listed above. However, the actual measured variables reflect daily practice and so are assumed to reflect similar confounding in daily assessments.

5. Analysis

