6.2.2 Secondary outcome

Secondary outcomes are death due to bleeding if available in the registry, early death (< 24 hours) and coagulopathy at hospital admission defined by an INR > 1.2 or TP $< 70\%$ or Fibrinogen ≤ 1.5 g/L (each other will be used for sensibility analysis)^{7,8,9}.

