5.3 Subgroup analyses

If the sample size permits, the investigators will conduct subgroup analysis in different subpopulations for the primary and secondary outcomes. The investigators will create the following subgroups in our MTP study:

- Subgroup 1: subdivide the population into two groups: with or without isolated severe traumatic brain Injury (TBI) with AIS HEAD ≥ 3 and AIS thorax/abdominal <3 and/or AIS lower extremity < 4 .
- Subgroup 2: subdivide the population into two groups: with or without anticoagulation treatment before trauma.

- Subgroup 3: subdivide the population into two groups: with or without trauma-induced coagulopathy.
- Subgroup 4: subdivide the dataset in prehospital settings and in-hospital settings.
- Subgroup 5: All analysis and results will be present into two subgroups: missing data imputed and missing data excluded with the complete case analysis.
- Subgroup 6: The investigators will test the heterogeneity of the performance parameters of each centre and the investigators will potentially exclude data from centre with homogeneous case mixes.
- Subgroup 7: subdivide the population into two groups: low-volume prehospital fluid replacement (<1500 ml) and High-volume prehospital fluid replacement (>1500ml).

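### Adding fibrinogen to an any-one-of definition of coagulopathy cannot counteract anticoagulant confounding through INR or TP

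*SAP*

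**What the plan says.** SAP 4.4 names the problem openly: "The trauma-induced coagulopathy as secondary outcome is assumed to be confounded by anticoagulant treatments". It then gives two responses. The first is the definition itself: "To counteract the confounding covariate, the investigators will include the fibrinogen < 1.5 g/L in the definition of trauma-induced coagulopathy". The second is a split: "The investigators will also define a subgroup of patients with anticoagulant treatment or not".

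The definition stands in SAP 6.2.2 (under 5.1): "coagulopathy at hospital admission defined by an INR > 1.2 or TP" below 70% "or Fibrinogen ≤ 1.5 g/L (each other will be used for sensibility analysis". I read the remark in brackets as a plan to analyse each criterion on its own as a sensitivity analysis. The protocol synopsis, under Outcome(s), has the same structure: "Coagulopathy at admission defined by INR > 1.2, quick TP < 70% or Fibrinogen < 1.5 g/L".

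SAP 5.2.1.1 applies the full set of performance measures to the secondary outcomes. SAP 5.3 lists the anticoagulant split as Subgroup 2 and a division "with or without trauma-induced coagulopathy" as Subgroup 3, with no separate definition for the latter. The section opens with a condition: "If the sample size permits, the investigators will conduct subgroup analysis in different subpopulations for the primary and secondary outcomes".

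**The concern.** The criteria are joined by *or* in both documents. A further *or* term can turn a negative into a positive but never a positive into a negative. It therefore cannot remove a patient whose INR or TP is abnormal because of a pre-injury anticoagulant. The plan identifies a confounder, states a correction, and the correction does not act on it.

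Two analyses are exposed. When the scores are assessed against coagulopathy, some cases are cases because of medication rather than injury. Subgroup 3, if it reuses the composite, puts these patients in the trauma-induced stratum. A reader of the SAP would believe that the confounding had been dealt with in the definition.

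**Working it through.** **No plan figure to reproduce.** The documents give no rate, power or sample size calculation for this outcome. The core of the check is logical. The rates below are assumptions and serve only to show scale.

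**Step 1: logic.** Take INR, TP and fibrinogen each as abnormal (1) or normal (0), which gives 8 patterns. The patterns that matter are those abnormal on INR and/or TP with normal fibrinogen: (1,0,0), (0,1,0) and (1,1,0).
- Under INR or TP, all 3 are cases.
- Under INR or TP or fibrinogen, all 3 are still cases, so 0 are removed.
- Only a rule that required low fibrinogen, alone or jointly with the others, would make these 3 negative. Neither document uses such a rule for the main outcome.

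**Step 2: share of composite positives that is purely drug-driven.** Let *a* be anticoagulant use, *t* the true frequency of trauma coagulopathy, and *d* the probability that the drug alone takes a user over the INR or TP cut. Assume independence, that the composite catches every true case, and that it has no other false positives. A drug-driven case is an anticoagulated patient without trauma coagulopathy who is over the cut.

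Share = a·d·(1−t) / [t + a·d·(1−t)]

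| a | t | d = 0.80 | d = 0.30 |
|---|---|---|---|
| 5% | 15% | 0.0340/0.1840 = 18.5% | 0.01275/0.16275 = 7.8% |
| 5% | 25% | 0.0300/0.2800 = 10.7% | 0.01125/0.26125 = 4.3% |
| 10% | 15% | 0.0680/0.2180 = 31.2% | 0.02550/0.17550 = 14.5% |
| 10% | 25% | 0.0600/0.3100 = 19.4% | 0.02250/0.27250 = 8.3% |
| 15% | 15% | 0.1020/0.2520 = 40.5% | 0.03825/0.18825 = 20.3% |
| 15% | 25% | 0.0900/0.3400 = 26.5% | 0.03375/0.28375 = 11.9% |

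The range is about 11–40% at d = 80% and about 4–20% at d = 30%.

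**Step 3: allowing imperfect criteria.** Use the planned 10,000 patients (SAP 3.2) and assume t = 25%, INR/TP sensitivity 80%, and low fibrinogen in 40% with and 2% without trauma coagulopathy. Vary use over 5–20% and d over 30–90%.
- Drug-driven cases, lowest: 10,000 × 0.75 × 0.05 × 0.30 = 112.5. Highest: 10,000 × 0.75 × 0.20 × 0.90 = 1,350. The count is the same with and without the fibrinogen term.
- All false positives among anticoagulated patients with the term, lowest: 375 × (1 − 0.70 × 0.98) = 117.75. Highest: 1,500 × (1 − 0.10 × 0.98) = 1,353. Both are slightly more than without it.
- True positives are 2,500 × (1 − 0.20 × 0.60) = 2,200. Low fibrinogen in other patients without coagulopathy adds 7,125 × 0.02 = 142.5 or 6,000 × 0.02 = 120.
- Drug-driven share: 112.5/2,460.25 = 4.6% up to 1,350/3,673 = 36.8%.
- Fibrinogen alone would give 375 × 0.02 = 7.5 up to 1,500 × 0.02 = 30 false positives in the same patients.

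**Step 4: possible effect on the C-statistic.** Suppose the true value is 0.80 (assumed) and drug-driven cases score like non-cases. With a drug-driven share *w*, the observed value is 0.80(1−w) + 0.50w. This gives about 0.79 at w = 4%, 0.77 at 11%, 0.74 at 20% and 0.68 at 40%. If anticoagulated patients score differently from other non-cases, these values shift.

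**The case against.** The best defence is that the plan does not rely on the definition alone. The single-criterion analyses in SAP 6.2.2 carry no condition, so a fibrinogen-only result, the one least exposed to the drug, is already planned. The anticoagulant split is stated in SAP 4.4 as something that will be done. At 10,000 patients and 5–15% use it would have 500–1,500 anticoagulated patients and at least 8,500 others. On this view the dispute is only about which analysis is called the main one. The formal outcome is also named coagulopathy at admission, which an anticoagulated patient with a raised INR does meet. The trauma-induced label appears only in SAP 4.4 and 5.3.

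Much of this stands, and it limits the point. It does not rescue the remedy: the main composite is unchanged, SAP 5.3 makes the split conditional on sample size, and Subgroup 3 uses the trauma-induced label with no other definition.

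A reader might infer more than the documents support:
- *That the fibrinogen term makes matters worse, or does the opposite of its purpose.* It leaves the drug-driven count unchanged and adds other cases. The share can even fall a little. With a = 10%, d = 80%, t = 15% and the Step 3 test properties, it goes from 0.068/0.188 = 36.2% without the term to 0.068/0.2156 = 31.5% with it.
- *That every anticoagulated case is misclassified.* Counting all of them gives 15–49% at d = 80%, but that includes patients who also have true trauma coagulopathy. The drug-only range is 11–40%.
- *That all the safeguards depend on sample size.* Only the subgroup analyses do.
- *That the main comparison of scores is compromised.* Massive transfusion is defined without any coagulation test.

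**Conclusion.** The point holds. The correction stated in SAP 4.4 fails by logic under the definition in both documents, whatever the rates. Its reach is one secondary outcome and, apparently, one of seven subgroups. The primary outcome is untouched, so this is a change that should be made rather than one on which the study depends.

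The size is uncertain because no rate is given in the documents. On the assumed 5–15% use and 15–25% true coagulopathy, purely drug-driven patients are about 4–20% of composite positives at 30% drug positivity and about 11–40% at 80%. Drug positivity is an influential assumption and should be read as a range. The loss of discrimination in Step 4 needs the further assumption that drug-driven cases score like non-cases.

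**What to change.** In the SAP:
1. Delete the statement in 4.4 that including fibrinogen counteracts the confounding.
2. Make the analysis in patients without pre-injury anticoagulants the firm, pre-specified main analysis of trauma-induced coagulopathy, not conditional on sample size. Use the same population as the basis of Subgroup 3.
3. Report anticoagulated patients separately, including the fibrinogen-only result already planned as a sensitivity analysis. Do not pool different outcome definitions from the two strata into one main outcome.
4. Keep the all-patient composite as a reported outcome, but call it coagulopathy at admission throughout.
5. Add pre-injury anticoagulant use to SAP Table 1. SAP 4.3.1 presents that table as the full request list, yet it has only a row for past medical history. The protocol's variable list combines anticoagulants with antiaggregants; request them separately.
6. State how missing anticoagulant status is handled, since it is not among the variables in the imputation model.
7. Reconcile the fibrinogen cut-off: strictly below 1.5 g/L in the protocol and SAP 4.4, at or below 1.5 g/L in SAP 6.2.2.

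The cost is mostly wording, because step 2 promotes one arm of the planned Subgroup 2, plus one item in the data request. The main coagulopathy analysis loses the anticoagulated patients and depends on how completely the registry records anticoagulant use. SAP 3.3 places registration of the plan before receipt of the data, so at that stage the change can be made without reference to results.

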5.1 Outcome definitions

6.1.1 Primary outcome

The primary outcome is the presence of massive transfusion (MT) in Swiss trauma patients, defined by a transfusion equal to or greater than 10 Red blood cell (RBC) in the first 24 hours or ≥ 3 RBC in the first hour if available in the Swiss Trauma Registry.

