
Measurements and procedures:
	
Predictive Variables:
 
Demographics: Age, gender, type of accident, mechanism of Injury (penetrating/blunt), Hospital (anonymised by number), Date and time of accident.
 
Prehospital settings: Arrival on scene (paramedics, date/time and medics, date/time), type of transport: physician staffed ambulance/helicopter, Firsts clinical measures recorded: Systolic blood pressure (SBP), Respiratory rate (RR), Heart Rate (HR), Pulse Oximetry, Glasgow coma scale, temperature, cardiopulmonary reanimation, Drugs Use: Tranexamic acid (Date/time) and vasoactive, early death before arriving to the hospital.
 
In-hospital settings (trauma room): Hospital arrival (date/hour), Firsts measures: Systolic blood pressure (SBP), Respiratory rate (RR), Heart Rate (HR), Pulse Oximetry, Glasgow coma scale, temperature, cardiopulmonary reanimation, Biological parameters: haemoglobin, Platelets, lactates, Base excess, TP (sec and %), INR, PTT, Fibrinogen, Drugs use: Tranexamic acid (date/time), vasoactive, Vitamin K, Fibrinogen, Prothrombin complex concentrate, rFVIIa, Red blood cell (number in the first hour, date/hour of each Red blood cell), platelets units, fresh frozen plasma.
 
Imaging: type of imaging, results: positive or negative for free fluid, date/time of imaging.
 
Diagnosis: AIS final, ISS final, Medical past, use of anticoagulant/antiaggregant before trauma
 
Outcome: Date/time of death, Early death (<12 hours), Early death (<24 hours), number of red blood cell in 24 hours, Massive transfusion (defined as ≥ 10 red blood cells in the first 24 hours).
 
Depending of the availability of requested variables in the registry, we will ask for complementary variables.
 
Comparison:
 
Performance comparison of pre-existing scores (TASH, ABC and BATT scores) in term of overall performance, discrimination and calibration.
 
Evaluation of clinical utility and feasibility in prehospital settings and emergency admission.

Intervention:
	
Comparison of score performances (Overall performance, discrimination and calibration)

Control Intervention (if applicable):
	
No group controls

Number of Participants with Rationale:
	
The number of participants will depend of the Swiss Trauma Registry Database. We project to include 10'000 participants for our study. A post-hoc power calculation will be performed.

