5.2.4. Calibration

Calibration is the agreement between observed and predicted outcomes. The investigators will mostly estimate calibration as the difference between the mean predicted and observed probabilities and the ratio of the predicted and observed number of events (P/O). The investigators will plot the observed and predicted probabilities of massive transfusion by decile of the score and with local regression based on LOESS algorithm. The investigators will estimate the calibration intercept and slope of the calibration plot as a measure of spread between predicted and observed outcome. Ideally, the intercept would be zero indicating that the predictions are neither systematically too low or too high and the slope would be 1.

Unfortunately, the investigators cannot estimate the calibration of the BATT score, because of its different outcome (death due to bleeding and not the massive transfusion as the TASH and ABC score). For the BATT, calibration will be assessed with the outcome of death due to bleeding or early death.

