Vitamin K (doses, date/time)		X	
rFVIIa		X	
Fibrinogen (doses, date/time)		X	
Platelets units (number, date/time)		X	
Red Blood Cell (number, date/time)		X	
prothrombin complex concentrate		X	
Fresh frozen plasma (number, date/time)		X	
Imaging			
Type of Imaging		X	
CT or FAST positive for free fluid		X	
Outcome			
Date and time of death			X
Early death (<12 hours)	X	X	X
Early death (< 24h)			X
Massive Transfusion (defined by 10 RBC/24h)			X
Diagnosis			
Code AIS		X	
Final ISS		X	
Scores			
TASH Score	X	X	
ABC Score	X	X	
BATT Score	X	X	

Table 2. Summarize of potential baseline characteristics.

Age, mean (SD)
 
 - ≥ 65 years old, N (%) - < 65 years old, N (%) 
Sex male, N (%)
 
Mechanism of Injury: N (%)
 
 - Penetrating - Blunt 
Circumstances, N (%)
 
 - Road traffic Injury 
 ➤ Car ➤ Motorcycle ➤ Bicycle ➤ Pedestrian ➤ Other (train, boat) - Fall 
 ➤ > 3 meters ➤ < 3 meters ➤ Unclear - Gunshot - Stabbing - Explosion - Avalanche - Other - Unknown 
Physician staffed ambulance, N (%)
	
Prehospital SBP, mean (SD)
 
 - SBP < 90 mmHg, N (%) - SBP >90 mmHg, N, (%) 
Prehospital HR, mean (SD)
 
 - HR > 120/min, N (%) - HR < 120/min, N (%) 
Prehospital GCS, N (%)
 
 - 3-8 - 9-12 - 13-15 
Prehospital CPR, N (%)
 
ISS mean (SD)
 
ISS by categories, N (%)
 
 - 9-15 - 16-24 - 25-34 - ≥ 35 
Overall AIS score ≥3, N (%)
 
Severe head injury (AIS head ≥3), N (%)
	
ABC score, mean (SD)
 
0-1, N (%)
 
2-4, N (%)
 
TASH score, mean (SD)
 
 - 0-17, N (%) - 18-31, N (%) 
BATT score, mean (SD)
 
 - 0-7, N (%) - 8-12, N (%) 
Death due to bleeding, N (%)
 
Massive transfusion, N (%)
 
Early Death (<24h), N (%)
 
 - < 12h, N (%) - 12-24 h, N (%)

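### The primary event is widened only if the registry holds first-hour transfusion counts, and TASH calibration is planned on that event alone, with no analysis by definition

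*SAP*

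**What the plan says.** The protocol synopsis (Outcomes) and SAP 5.1 (6.1.1 Primary outcome) agree. The protocol has "Massive transfusion defined by a transfusion equal to or greater than 10 Red blood cell (RBC) / 24 hours or ≥ 3 RBC", where the 3 units are those given within one hour, and the SAP makes this second route conditional: "≥ 3 RBC in the first hour if available in the Swiss Trauma Registry".

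SAP 4.4 gives the reason. Some patients die before they can receive 10 units, so "the investigators add in the massive transfusion definition the use of ≥ 3 RBC administered in the first hour", again on condition that the registry has the variable.

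The variable lists use a narrower label. The protocol (Measurements and procedures) has "Massive transfusion (defined as ≥ 10 red blood cells in the first 24 hours", and SAP Table 1 has "Massive Transfusion (defined by 10 RBC/24h". The same lists request the inputs for the first-hour route: "Red blood cell (number in the first hour, date/hour of each Red blood cell" in the protocol and "Red Blood Cell (number, date/time" in SAP Table 1.

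SAP 5.2.1 and 5.2.4 assess calibration against massive transfusion by mean difference, predicted-to-observed ratio (P/O), intercept and slope. For BATT, SAP 5.2.4 says the investigators "cannot estimate the calibration of the BATT score, because of its different outcome"; it treats TASH and ABC as matching the outcome. The SAP plans a sensitivity analysis by definition for coagulopathy (6.2.2) but none for massive transfusion.

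**The concern.** SAP 3.3 commits to posting the plan before the dataset is received, and SAP section 7 gives avoidance of data-driven results as an aim. A primary event whose content is settled by what the extract contains works against both.

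The choice also matters numerically. TASH risks come from a fixed table (SAP Figure 1), so the predicted number of events does not move when the observed event is widened. The event rate, Brier score, P/O and calibration intercept all depend on which definition ends up in force. If the wider event is not the one TASH was built to predict, the paper could report under-prediction that comes from the outcome definition and not from the score. With only one definition analysed, a reader could not tell the two apart.

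**Working it through.** The documents give no event rate and no sample-size calculation, so there is no stated figure to reproduce. The check has two parts.

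**1. Set logic.** Let A be at least 10 units in 24 hours and B at least 3 units in the first hour. The primary event is A if B is not held, and A or B if it is. Every A case is also a composite case. Observed events O can therefore only stay the same or rise when B is added, while predicted events P stay fixed. P/O can only stay the same or fall, and the intercept can only stay the same or rise. Extra events can come only from patients with 3 to 9 units in 24 hours.

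**2. Size, under stated assumptions.** Assume that TASH is exactly calibrated to A, that A has prevalence p, and that B adds a fraction f of extra events. None of these is in the documents. N = 10,000 is the projection in SAP 3.2.

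- P = N·p and O = N·p·(1+f), so P/O = 1/(1+f), whatever p is.
- Standard error of log O = √((1 − O/N)/O); 95% CI = P/O × exp(±1.96 × SE).
- Example, p = 5%, f = 25%: P = 500, O = 625, P/O = 500/625 = 0.80. SE = √(0.9375/625) = 0.0387, giving a CI of 0.74 to 0.86.
- Intercept shift with slope fixed at 1: the TASH table for 9 to 23 points is fitted closely by logit(p) = −5.456 + 0.303 × TASH. The shift was solved numerically over an assumed negative binomial distribution of TASH points (mean 5.0, giving mean risk 5%).

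| Extra events f (assumed) | Observed events, p = 5% | P/O | 95% CI, p = 5% | Mean predicted minus observed | Intercept shift |
|---|---|---|---|---|---|
| 0 | 500 | 1.00 | 0.92–1.09 | 0 | 0 |
| 10% | 550 | 0.91 | 0.84–0.99 | −0.5 points | +0.14 |
| 25% | 625 | 0.80 | 0.74–0.86 | −1.25 points | +0.33 |
| 50% | 750 | 0.67 | 0.62–0.71 | −2.5 points | +0.60 |
| 100% | 1,000 | 0.50 | 0.47–0.53 | −5 points | +1.05 |

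(Points are percentage points.)

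**Sensitivity.** The intercept depends on the assumed spread of risk. A normal linear predictor with SD 1.6 and mean risk 5% gives +0.28, +0.52 and +0.91 for f = 25%, 50% and 100%. P/O does not depend on this. At p = 3% and f = 10% the CI is 0.82 to 1.01 and includes 1. From f = 25% upward it excludes 1 at p = 3%, 5% and 10%.

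**The case against.** Several stronger readings are tempting and are not supported.

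- **That some patients are judged on two routes and others on one.** SAP 4.4 ties the condition to whether the registry has the variable, which most naturally sets one rule for everyone. Uneven recording of the first-hour count between centres is possible, but the documents neither show it nor address it.
- **That the documents hold two rival primary outcomes.** Every passage that sets the outcome agrees. The narrower wording stands in lists of variables to obtain, and those lists also request the inputs for the first-hour route. This is a label to align, not missing data.
- **That TASH calibration is certainly wrong.** SAP Figure 1 speaks only of massive transfusion without defining it. Whether the composite departs from TASH's own target has to be confirmed from the cited source.
- **That the treatment of BATT is a flat contradiction.** BATT predicts death, a different kind of event. A changed threshold for massive transfusion is a smaller departure, so the inconsistency is one of degree.

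The added route is also disclosed and has a sound purpose: the 24-hour count alone misclassifies early deaths, so simply reverting to it would bring that problem back. The size is illustrative too, since small f gives a small effect.

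These objections narrow the point but do not remove it. With first-hour data present, the plan calibrates TASH only on an event the SAP itself says was enlarged, and offers no second view.

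**Conclusion.** The point stands in conditional form. The primary event is left open until data receipt, its label is inconsistent in the variable lists, and no analysis by definition is planned.

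The direction of the effect on P/O and the intercept is certain. Its size is not, because the documents give no extra-event fraction, prevalence or TASH risk distribution. If first-hour data are available and TASH predicts the 24-hour event, P/O for a well-calibrated score runs from 0.91 to 0.50 as extra events go from 10% to 100%. At the projected 10,000 patients, extra events of 25% or more would be read as clear under-prediction at each prevalence tried. If first-hour data are not available, the outcome reverts to the 24-hour count and the calibration problem disappears. That dependence is itself the reason to fix the definition now. This should be corrected, but it does not undermine the study.

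**What to change.** Before data receipt:

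1. Define two fixed outcomes: MT-24h (at least 10 units in 24 hours) and MT-composite (either route). State which is primary. The composite may stay primary for the reason in SAP 4.4.
2. Align the protocol outcome section and variable list, SAP 5.1 and SAP Table 1 with these names.
3. Report TASH Brier score and calibration on both outcomes, and read calibration on the one that matches the definition in TASH's source, once confirmed. Report discrimination on both.
4. For the composite, count anyone with at least 10 units in 24 hours as an event whether or not a first-hour count is recorded. Count anyone with fewer than 3 units in 24 hours as a non-event. Treat a missing first-hour count as missing only in the remaining patients. State how it is handled, because SAP section 5.2.1 (Imputation method) covers predictors only, and report its frequency by centre. Restricting the composite to patients with a recorded count would drop certain events.

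The cost is SAP wording and one additional set of results, repeated across the imputed and complete-case analyses. Timed red cell data are already requested.
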